Various techniques have been used for the dissection of LIMA, still studies say 40% of LITA gets damaged or has a poor flow, owing to spasm and injury.³ To curtail this, various vaso-active agents have been studied to reduce stress and increase the flow rate of LIMA, during dissection.²C02, because of the hypercapnic veno-dilator properties was utilized in a few studies from 1988.⁴ and proved to have promising results, though the instrumentation for the same has not been devised. We have planned to use a modified technique as per a case report done by shigu et al. (2017)⁵ in a larger study; to study the efficacy of carbo-dissection for LIMA harvesting.

RESEARCH QUESTION

Does the use of modified carbodissection result in less operative time and increased flow rate in harvesting of LIMA.

AIMS & OBJECTIVES:

AIM: To study the flow rate and operative time of modified carbo-dissection for harvesting of Left Internal Mammary artery.

Objectives of the study:

1. To study the first flow in one min, operative time of conventional pedicled technique and modified carbodissection technique for harvesting LIMA

TYPE OF STUDY

Prospective comparative study

PERIOD OF STUDY : Jan 2021- Jan 2022

DURATION OF STUDY: 12 months

 PLACE OF STUDY
 : Department of Cardiovascular and Thoracic Surgery,

 Government Medical College, Kottayam

STUDY POPULATION

Patients undergoing elective CABG in GMC, Kottayam with requirement of LIMA harvest in the dept. of Cardiovascular & Thoracic surgery, Govt. Medical college, Kottayam.

RESEARCH APPROACH

Quantitative

Statistical analysis:

Data will be entered into Microsoft excel data sheet and will be analyzed using SPSS 22 version software. Categorical data will represented in the form of Frequencies and proportions. Chi-square will be the test of significance. Continuous data will be represented as mean and standard deviation. Independent t test will be the test of significance to identify the mean difference between two groups. p value <0.05 was considered as statistically significant.

Sample Size:⁶⁻⁹ Was estimated by using the difference in first free flow measurement in the carbon dioxide–insufflated internal thoracic arteries in Group 1.28 ± 19 mL/min and in group 2 was 60 ± 32 mL/min; from the study Mehmet O zkan et. al.⁴ Using these values at 99% Confidence limit and 90% power sample size of 21 was obtained in each group by using the below mentioned formula and Med calc sample size software. With 10% non-response sample size of $21 + 2.1 \approx 23$ cases will be included in each group.

Sample Size Estimation Formula:

Sample size =
$$\frac{2SD^2(Z_{\alpha/2} + Z_{\beta})^2}{d^2}$$

SD – Standard deviation = From previous studies or pilot study $Z_{\alpha/2} = Z_{0.05/2} = Z_{0.025} = 1.96$ (From Z table) at type 1 error of 5% $Z_{\beta} = Z_{0.20} = 0.842$ (From Z table) at 80% power d = effect size = difference between mean values So now formula will be Sample size = $\frac{2\text{SD}^2(1.96 + 0.84)^2}{d^2}$

Alpha	Zα (One tailed)	Za/2 (two tailed)
0.20	0.84	1.28
0.15	1.04	1.44
0.10	1.28	1.64
0.05	1.64	1.96
0.01	2.33	2.58
0.001	3.09	3.29

Power	Z _{1-β}
0.70	0.52
0.75	0.67
0.80	0.84
0.85	1.03
0.90	1.28
0.95	1.64
0.99	2.33

Sample Size For Comparing Two Means

	•						
Confidence Interval (2-sided) Power Patio of complexize (Croup 2/Croup 1)							
	Group 1		Group 2	Mean difference ¹			
Mean	28		60	-32			
Standard deviation	19		32				
Variance	361		1024				
Sample size of Group 1		21					
Sample size of Group 2		21					
Total sample size		42					

Input Data

¹ Mean difference= (Group 1 mean) - (Group 2 mean)

Randomization:

Computer generated randomization using www.randomization.com for the allotment of case between two groups, details as mentioned below.

A Randomization Plan

from

http://www.randomization.com

1.	B		_
2.	В		_
З.	A		-
4.	В		 -
5.	В		-
6.	В		 -
7.	A		 -
8.	A		-
9.	A		-
10	•	A	-
11	•	B	
12	•	A	
13	•	B	
14	•	В	
15	•	B	
16	•	A	
17	•	A	
18	•	B	
19	•	A	
20	•	A	
21	•	A	
22	•	B	
23	•	B	
24	•	A	
25	•	B	
26	•	A	
27	•	A	
28	•	A	
29	•	B	
30	•	A	
31	•	B	
32	•	B	
33	•	A	
34	•	B	
35	•	A	
36	•	В	
37	•	A	
38	•	В	
39	•	B	
40	•	A	
4⊥	•	A	
42	•	В	
43	•	A	
44	•	В	
45	•	В	
46	•	Α	

46 subjects randomized into 1 block To reproduce this plan, use the seed 29386 along with the number of subjects per block/number of blocks and (case-sensitive) treatment labels as entered originally. Randomization plan created on 12/2/2020, 11:36:59 PM

HYPOTHESIS:

Use of modified carbodissection for harvesting will result in better flow rate and less operative time.

MATERIALS AND METHODS

STUDY PROCEDURE

After taking informed consent, patients with CAD with indication for CABG and satisfying the inclusion criteria will be admitted, data will be collected on predefined proforma.

Methodology

Following consultation to our department, after a detailed history and clinical examination, patients with CAD, being planned for CABG, will be subjected to a detailed pre-op Echocardiogram and coronary angiogram. After necessary pre-op assessment, patient will be taken up for the surgery. Invasive monitoring will be done. After median sternotomy, pericardiectomy, LIMA dissection will be done by the planned method as in: The modified carbodissection technique is performed using an improvised instrument that combines an electrocautery pencil (Valleylab[™] Force FX electrocautery Pencil, Covidien, USA) with a CO2 mister blower (PerfX® Heart Lung pack Blower/Mister Kit, B L lifesciences, Noida, India) that is routinely used in off-pump CABG. The instruments are fixed together using silk ties. The electrocautery is used in the coagulation mode at a setting of 10 to 15. The CO2

flow is set at 2 to 3 liters/minute. Saline flow is adjusted to a level where it does not hinder the effective coagulation but still prevents drying and desiccation of the tissues.⁵

Following dissection of LIMA by the above mentioned technique, flow of blood from the harvested LIMA, for one whole minute is noted. The operative time required for the dissection of LIMA will be noted and entered.

STUDY TOOLS

Structured Proforma

Instruments -

- 1. Gas blower/mister (PerfX® Heart Lung pack Blower/Mister Kit, B L lifesciences, Noida, India)
- Electrocautery (Valleylab[™] Force FX electrocautery Pencil, Covidien, USA)
- 3. C02 supply

INCLUSION CRITERIA

- 1. Elective CABG
- 2. Hemodynamically stable CAD patients

EXCLUSION CRITERIA

- 1. Re-operation, previous sternotomy (where LIMA is already dissected)
- 2. concomitant valve operation, ventricular aneurysm resection
- 3. other additional major cardiac procedures
- 4. Patients with chronic obstructive pulmonary disease

DATA MANAGEMENT AND STATISTICAL ANALYSIS

Data will be coded and entered in Microsoft Excel and analyzed using IBM SPSS software Qualitative data will be presented using percentage and 95% CI, and analyzed with chi square test of independence. Quantitative data will e presented using mean and standard deviation.

Independent t-test will be used for comparison between groups. Pearson's correlation coefficient will be used to test the relationship between parameters. A p value < 0.05 is used as threshold for significance.

LIMITATIONS OF STUDY:

Small sample size Skill dependent

PRINCIPAL INVESTIGATOR: [name]

REVIEW OF LITERATURE

Over the period of years, the internal thoracic artery or internal mammary artery has become the main conduit of choice for coronary artery bypass grafting; based on its superior patency rates and longer survival period.⁴ A proper functioning LIMA grafted to LAD, provides a patency rate of 98% at 1 year and 94% at 7 years, compared to a patency rate of only 75% at 5 years for saphenous vein graft.¹ The operative technique used for the dissection of ITA, might affect the flow capacity⁴ Different techniques have been tried over the period of years for LIMA dissection and most commonly used are the pedicled, skeletonised/semi-skeletonised technique. But still studies have shown a failure rate of LIMA failure is high at 40%.³ Nevertheless, the thoracic wall damage and sternal infection are present. To counter-act this reduced flow rates due to spasm and injury, various vaso-active agents have been used in the yester years. The most commonly used is a topical (or) intra-luminal vaso-dilator namely papaverine. Use of gaseous vaso-dilators, has not been studied in detail and the safer of all is Carbon dioxide(C02), due to its easy diffusion and non inflammable properties, has more vaso-dilatory properties Both *in vitro* and *in vivo* studies have demonstrated a rightward shift of the oxygen–hemoglobin dissociation curve after administration of CO₂. Sakai *et al.* described this as an "artificial Bohr-effect". This was responsible for the increased partial pressure of oxygen and the decreased pH.⁷

A few studies have combined the use of C02 insufflation in LIMA dissection, as a gaseous vaso-dilator to avoid injury. In 1988, Myles Edwin Lee, used the C02 insufflation technique called carbo-dissection and in this technique, C02 is injected into the endothoracic fascia to form subpleural emphysema bleb, to aid in the dissection of LIMA. Methodology used was Cardiac pacing lead introducers (8F to 12F), initially modified by placing four to six side holes within a centimetre of the tip, are now used as obtained from themanufacturer but with the tip flattened to give an elliptical cross-section for easy passage through tissue. An 8Fintroducer, now our standard, is attached to a commercially available gas delivery system (Gish Biomedical, Santa Ana, CA), which includes a Luer lock connector, 0.6-cm (%-inch) polyvinylchloride tubing, and a 0.45-kmgas filter (Model No., Gas-1) (Fig l), all of which are brought to the operative field with the pump tubing and connected to a tank of C02 by the perfusionist. A small incision is made in the endothoracic fascia medial to the ITA pedicle and adjacent to the superiorborder of a costal cartilage. The incision should bejust long enough to accommodate the introducer and not allow gas leaks into the atmosphere. A flow of 4 to 6L/min suffuses the chest wall for distances of 10 cm laterally, superiorly, and inferiorly, in approximately 2 seconds. In another study conducted by ozakan et al,

employed the use of subpleural emphysema with 24G needle, thereby forming a bleb to clearly dissect. The study was done on 28 consecutive patients and had no incidence of complications.

An another descriptive study by O[°] zkan et al, described the use of carbodioxide insufflations in 350 patients and no incidence of complications was reported.⁸ As this technique seems tedious and injury to LITA, due to the insufflate needle is still present. An improvised technique as described by shigu et al⁵, published in 2017, which uses a modified technique on carbo-dissection : technique is performed using an improvised instrument that combines an electrocautery pencil with a CO2 mister blower. The instruments are fixed together using silk ties. The electrocautery is used in the coagulation mode at a setting of 10 to 15. The CO2 flow is set at 2 to 3 liters/minute. This method is relatively easier to perform, with no excessive use of resources. Therefore this was taken to be used in own study of dissection of LIMA.

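### Minor: 23 per group gives about 87% to 88% power at two-sided 1% after the stated loss, not 90%; at the planned 5% threshold it gives about 96% to 97%

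*Combined protocol and SAP*

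**What the plan says.** The Sample Size section takes first free flow as the basis, with means of 28 and 60 mL/min and SDs of 19 and 32, and concludes: "Using these values at 99% Confidence limit and 90% power sample size of 21 was obtained in each group". The calculator table in the same section is headed as two-sided ("Confidence Interval (2-sided") and also gives 21 per group, 42 in total. The allowance for loss follows: "With 10% non-response sample size of" 21 + 2.1, rounded to 23. The randomisation list agrees with that: "46 subjects randomized into 1 block", with 23 A and 23 B.

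The formula printed between the text and the table is worked at a different setting, 5% type 1 error and 80% power.

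For the analysis, the Statistical analysis section says: "Independent t test will be the test of significance to identify the mean difference between two groups". The Data Management and Statistical Analysis section sets the level: "A p value < 0.05 is used as threshold for significance". The 1% level appears in the sample-size calculation and nowhere in the analysis plan.

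**The concern.** Two steps in the calculation push the same way. First, the loss allowance adds 10% to the required number instead of dividing by the 90% expected to remain, so the number enrolled does not quite preserve the 21 the plan asks for. Second, the formula uses normal quantiles, while the analysis uses a t-test. With about 20 patients per group and a 1% level, the t critical value is noticeably larger than the z value (2.70 against 2.58 with 21 per group).

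The power statement is a figure that the trial report will probably repeat. If it is too high for the design as planned, it should be corrected before it is quoted.

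**Working it through.** **Inputs.** All come from the Sample Size section unless noted: difference 60 − 28 = 32 mL/min; SDs 19 and 32; two-sided alpha 0.01; power 0.90; loss 10%; 23 enrolled per group. The test (independent t) and the threshold (p < 0.05) come from the two statistical analysis sections.

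**1. Reproduce the plan's figure.**
n = (SD₁² + SD₂²)(z₀.₉₉₅ + z₀.₉₀)² / d² = (361 + 1024)(2.5758 + 1.2816)² / 32² = 1385 × 14.88 / 1024 = 20.12, so 21. The plan's tabulated values (2.58 and 1.28) give 20.15, also 21. The stated 21 is reproduced. The formula as printed, at 5% and 80%, would give 10.6, so 11; it is not the source of the 21.

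**2. Loss.**
23 × 0.9 = 20.7 evaluable per group. To keep 21: 21 / 0.9 = 23.3, so 24. The difference is one patient per group.

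**3. Power with the planned test.**
For the equal-variance t-test the pooled SD is √(1385 / 2) = 26.3, the noncentrality is 32 / (26.3 × √(2/n)), and the degrees of freedom are 2n − 2. The Welch column uses the unequal-variance version.

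| Evaluable per group | z, 1% | t, 1% | Welch, 1% | t, 5% |
|---|---|---|---|---|
| 20 | 89.8% | 86.4% | 85.6% | 96.3% |
| 20.7 | 90.9% | 87.9% | 87.1% | 96.8% |
| 21 | 91.4% | 88.5% | 87.7% | 97.0% |
| 22 | 92.7% | 90.3% | 89.6% | 97.6% |
| 23 | 93.9% | 91.8% | 91.2% | 98.1% |

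Simulated normal data with the unequal SDs (200,000 trials per size) agree: at 1% the t-test gives 86.3% with 20 per group, 88.4% with 21 and 91.6% with 23.

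**4. Averaged over random loss.**
Assume that each patient is lost independently with probability 10%; this model is mine, not the plan's. Simulated power from 23 per group is then about 87.5% at 1% (86.6% with Welch) and 96.6% at 5%.

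**5. Where the shortfall comes from.**
At 21 per group, moving from z to t lowers power from 91.4% to 88.5%, or 2.9 points. Moving from 21 to 20.7 with the t-test lowers it from 88.5% to 87.9%, or 0.6 points. Most of the gap is z against t; the loss step is small.

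**6. Number needed for 90% at 1%.**
With the equal-variance test, 22 evaluable: 22 / 0.9 = 24.4, so 25 enrolled per group. With Welch, 23 evaluable: 23 / 0.9 = 25.6, so 26.

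**The case against.** The strongest reply is that the plan does what it says. It names its formula, and that formula gives 21. A normal approximation before a t-test is common practice. By that formula 20.12 are needed, 20.7 still meets this, and z power at 20.7 is 90.9%. Even with the t-test, 21 completers fall only 1.5 points short of 90%. All of this stands, and it is why the point is minor. It does not rescue the stated figure, because the test to be run is the t-test and the plan itself expects 10% loss.

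The second reply is that no analysis is planned at 1%. That also stands, and it limits the consequence. A reader might infer that the trial is underpowered because 23 enrolled do not protect 21 evaluable. The documents do not support that: the test is judged at p < 0.05, where the same inputs give 96.3% with 20 per group and 97.0% with 21.

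A reader might also make much of the chance that at least one arm ends below 21, which is 65% under independent 10% loss per patient. That loss model is an assumption absent from the documents. Flow and dissection time are both recorded during the operation, and the plan does not say how non-response would arise. Falling just below 21 also costs little power.

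The third reply is that the effect size matters far more than this rounding. That is true. The Review of Literature quotes 68 ± 46 versus 53 ± 32 mL/min from the same reference, a difference of 15. On those figures 23 per group would have about 24% power at 5%. The documents do not make clear which comparison the 28 and 60 represent. That is a separate and larger question, but it means any restated power must be given as conditional.

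**Conclusion.** The point holds as a minor correction. The claim of "99% Confidence limit and 90% power" is slightly too high for the design as planned: with 23 enrolled, 10% lost and an independent t-test, power at two-sided 1% is about 87% to 88%, and about 87% with the unequal-variance version. The gap of about 2 to 3 points is mostly z against t; the loss allowance costs one patient per group. The 21 is not a miscalculation by the stated formula, and the planned comparison at p < 0.05 is not underpowered for this reason, with about 96% to 97% after loss.

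These figures assume roughly normal flows, SDs of 19 and 32, and a true difference of 32 mL/min. The 32 mL/min is the least secure of these.

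**What to change.** Replace the power statement in the Sample Size section with wording such as: *23 per group, about 20.7 evaluable after 10% loss, gives about 96% to 97% power with the independent t-test at the planned two-sided 5% level (about 87% to 88% at two-sided 1%), if the true difference is 32 mL/min with SDs 19 and 32.*

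In the same edit:
- Use one alpha and one power throughout the section, consistent with the p < 0.05 threshold, in place of 99%/90% in the text and 5%/80% in the worked formula.
- Say which comparison the 28 and 60 mL/min represent, and reconcile the 32 mL/min difference with the 68 ± 46 versus 53 ± 32 mL/min in the Review of Literature.
- State whether the equal-variance or unequal-variance t-test will be reported, since the assumed SDs differ.

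The power restatement costs one sentence and no patients; the other edits are short clarifications. If the sponsor prefers to keep 90% at 1%, the arithmetic gives 25 per group (equal-variance) or 26 (unequal-variance). Nothing in the analysis plan requires that level.

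### The full 46-slot allocation list and its seed are printed in the protocol with no concealment step, so the next arm can be known before a patient is enrolled

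*Combined protocol and SAP*

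**What the plan says.** The Randomization section of the combined protocol and SAP states that a web-based generator is used "for the allotment of case between two groups, details as mentioned below". What follows is the list itself: slots 1 to 46, each labelled A or B, then "46 subjects randomized into 1 block To reproduce this plan, use the seed 29386" and the remaining settings needed to regenerate it, "along with the number of subjects per block/number of blocks and (case-sensitive) treatment labels as entered originally". The footer reads "Randomization plan created on 12/2/2020".

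The study period is given as "PERIOD OF STUDY : Jan 2021- Jan 2022", so the list predates the start whichever way the date is read (12 February or 2 December 2020). The study population is "Patients undergoing elective CABG in GMC, Kottayam with requirement of LIMA harvest".

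The Study Procedure section describes entry as follows: "After taking informed consent, patients with CAD with indication for CABG and satisfying the inclusion criteria will be admitted". The Methodology section then goes directly to dissection by the planned method. Neither says who holds the list, when the arm is disclosed, or that patients are taken consecutively.

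On analysis, the plan offers chi-square tests, Pearson correlation and, for the main comparison, "Independent t-test will be used for comparison between groups". The limitations name the small sample and dependence on skill, but not open allocation.

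**The concern.** Randomisation removes selection bias only if those who decide whether and when a patient enters cannot know the next assignment. Here the protocol itself discloses the sequence. That goes beyond a missing detail: a safeguard recorded elsewhere would not undo it unless the printed list were also replaced.

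Three features of this trial make disclosure matter. Cases are elective, so their order can in principle be changed. The harvesting technique is visible to the operating team, so although the text does not say which technique is A, the first case reveals it. And the plan concedes that results depend on skill, so advance knowledge would also allow operators to be matched to arms, which bears directly on dissection time.

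At stake are both stated outcomes, first flow over one minute and operative time. None of the planned analyses is stated to examine enrolment order, operator or access to the list.

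**Working it through.** **1. The plan's own figures.** Counting the printed list gives 46 entries, 23 A and 23 B. This agrees with the stated 46 subjects and with 23 per group (21 + 2.1 = 23.1, taken as 23).

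**2. How much can be foreseen.** With the list in hand, 46 of 46 arms are known. For comparison, suppose the same single block were concealed and only past arms were known. The best strategy is to guess the arm with more slots left. With a A-slots and b B-slots remaining, the expected number of correct guesses is

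E(a,b) = max(a,b)/(a+b) + [a/(a+b)]·E(a−1,b) + [b/(a+b)]·E(a,b−1), with E(0,0) = 0.

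This gives E(23,23) = 26.77, and 26.77/46 = 58.2%. The same recursion gives 70.8% for fixed blocks of 4 and 68.3% for blocks of 6. The single block is therefore not the fault; the disclosure is.

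**3. What a given bias would do to the planned test.** Inputs:
- n = 23 per arm and two-sided alpha 0.05, from the plan.
- Planning SDs of 19 and 32 mL/min from the Sample Size section, giving a pooled SD of √((361 + 1024)/2) = 26.3 mL/min.
- The bias sizes are assumptions.

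With no true effect and a bias of δ SD, the t statistic on 44 degrees of freedom has noncentrality δ·√(23/2).

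| Assumed bias (SD) | mL/min | Noncentrality | False-positive rate |
|---|---|---|---|
| 0 | 0 | 0 | 5.0% |
| 0.1 | 2.6 | 0.34 | 6.3% |
| 0.25 | 6.6 | 0.85 | 13.2% |
| 0.5 | 13.2 | 1.70 | 38.2% |

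**4. What bias the printed list could produce.** Working down the list, there are 18 non-overlapping adjacent pairs with opposite arms. In each, exchanging the order of two patients exchanges their arms. Suppose k pairs are ordered so that the patient with the higher value of a preoperative predictor goes to one chosen arm, and the predictor has correlation ρ with the outcome. The expected gap between the higher and lower of two standard normal values is 2/√π = 1.128, so

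bias = (k/23) × 1.128 × ρ.

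For example, k = 9 and ρ = 0.3 gives (9/23) × 1.128 × 0.3 = 0.13 SD. False-positive rates come from simulation on the printed list (100,000 runs per setting, no true effect). Both k and ρ are assumptions.

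| Pairs reordered | ρ | Bias (SD) | mL/min | False-positive rate |
|---|---|---|---|---|
| 0 | any | 0 | 0 | 5% |
| 9 | 0.3 | 0.13 | 3.5 | 7% |
| 9 | 0.5 | 0.22 | 5.8 | 11% |
| 18 | 0.3 | 0.26 | 7.0 | 14% |
| 18 | 0.5 | 0.44 | 11.6 | 32% |

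Even with all 18 pairs reordered and ρ = 0.5 the bias stays below 0.5 SD, so the last row of the previous table is an extreme case.

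**5. Against the planning difference.** The plan expects 60 − 28 = 32 mL/min. The 9-pair bias is 3.5/32 = 11% to 5.8/32 = 18% of that. Against the 15 mL/min difference (68 − 53) that the literature review quotes, it is 3.5/15 = 23% to 5.8/15 = 39%.

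**The case against.** The strongest reply is that the documents show a possibility and not an event. The footer dates the list, not the protocol, and nothing says that those enrolling or scheduling patients consulted it. This stands as a limit on the claim. However, the protocol is written in the future tense, and it describes no barrier between the list and the people using the protocol.

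The size of the bias is also assumed. The documents name no preoperative predictor of flow and describe no reordering. Reordering all 18 pairs in the same direction would be systematic steering, not unconscious drift, so the 9-pair figures are the fairer illustration. Biases of that size could not by themselves produce the planned 32 mL/min difference. All of this is accepted; they could still create or inflate a smaller difference.

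Baseline tables by arm might be produced under the general chi-square and t-test wording. That is possible but not stated, and such tables would not show enrolment order or access to the list. Finally, a concealment step might sit in a part of the document that was not available for review. Even so, it could not conceal a list that the protocol prints.

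**Conclusion.** The concern holds. As written, the plan discloses every allocation in advance (46 of 46, against an expected 58% under concealment) and describes nothing to prevent that knowledge from influencing who is enrolled, when, or who operates. The comparison therefore cannot rely on randomisation to exclude selection bias.

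The disclosure is read directly from the text. The consequence for the results is conditional: about 7% to 11% false positives if 9 pairs were reordered, and 14% to 32% if all 18 were, with assumed correlations of 0.3 to 0.5. No steering is shown to have occurred. This must be fixed while the protocol can still be amended. Once recruitment has ended it can only be disclosed, because no analysis restores concealment afterwards.

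**What to change.** **Before recruitment.** Withdraw the printed list and seed and generate a new sequence; one block of 46 is acceptable if concealed. Keep the sequence and seed out of the protocol, with an existing colleague who neither enrols nor operates. Release assignments in sequentially numbered, sealed, opaque envelopes, each opened only after consent, eligibility and the operator have been recorded. State this in the Randomization section.

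**If recruitment is under way.** Do the same for the remaining slots, using the A and B counts still to be filled so that 23 per arm is preserved.

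**If recruitment has started or finished** (the stated period ends in January 2022). Report who had access to the list and when. Compare actual allocations, in enrolment order, with the printed list. Tabulate enrolment order, operator and baseline characteristics by arm, and add the lack of concealment to the limitations. This is a partial check, not a correction: agreement with the list would not reveal patients reordered before enrolment.

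**Cost.** A short amendment, a new list, at most 46 envelopes and a little of a colleague's time, with no extra patients or visits. For a finished study, only the disclosure, the comparison with the list and the table apply.

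### Conduit injury, thoracic wall damage and sternal infection are named as harvest harms but are not outcomes, so carbodissection could be reported as better despite more harm

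*Combined protocol and SAP*

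**What the plan says.** **Rationale.** The opening background states that "still studies say 40% of LITA gets damaged or has a poor flow, owing to spasm and injury". On harvest techniques in use, the Review of Literature adds: "Nevertheless, the thoracic wall damage and sternal infection are present". It then describes the earlier CO2 insufflation method and, just before adopting the modified technique, remarks: "As this technique seems tedious and injury to LITA, due to the insufflate needle is still present".

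**Outcomes.** The Research Question, the Aim, the single Objective and the Hypothesis concern only flow and operative time. The Methodology matches them: flow from the harvested LIMA is noted over one minute, and "The operative time required for the dissection of LIMA will be noted and entered". Data go on a predefined proforma whose fields are not set out.

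**Analysis.** The Statistical analysis section says of categorical data: "Chi-square will be the test of significance". The later Data Management and Statistical Analysis section adds percentages with 95% CI. Neither section names a categorical outcome.

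**Safety evidence cited.** One CO2 insufflation series is described thus: "The study was done on 28 consecutive patients and had no incidence of complications". A second, of 350 patients, is also reported as free of complications. The tested instrument is different: a cautery pencil tied to a mister blower. The opening background attributes it to a case report.

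**The concern.** Part of the reason for the trial is that harvesting damages the conduit, and part of the reason for choosing this variant is that the needle method can injure the artery. Both measured outcomes are complete once the conduit has been harvested and its flow read. Three kinds of harm can escape them:

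1. Injury that does not lower free flow over one minute.
2. A conduit damaged or discarded so that no flow is read. The plan has no rule for its flow value.
3. Sternal infection, which appears after the operation.

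The zero-complication series do not fill the gap. They used insufflation, the first through a needle, and not the improvised instrument tested here. A randomised comparison is the natural place to collect harm data on that instrument. If the plan does not ask for them, a favourable conclusion on flow and time would say nothing about these harms.

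**Working it through.** **Inputs.** From Sample Size: means 28 and 60 mL/min, SDs 19 and 32 (variances 361 and 1024), difference 32, 99% confidence two-sided, 90% power, 21 per group, 23 after 10% non-response. From both analysis sections: significance threshold 0.05. Assumed: the number of conduits lost, since the documents give no injury rate.

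**1. The plan's own figure.** n = (361 + 1024)(2.58 + 1.28)² / 32² = 1385 × 14.90 / 1024 = 20.1, rounded up to 21. This reproduces the stated figure, and 21 + 2.1 gives the stated 23. (The 5%/80% formula printed in the same section would give 10.6, so 11, and is not the source of the 21.)

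**2. How far lost conduits would pull down the flow result.** Suppose k of 23 carbodissection conduits are scored as zero flow, the rest follow 60 (32), and the conventional arm follows 28 (19) with none lost. With f = k/23:

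- mean m = 60(1 − f)
- variance v = (1 − f)(32² + 60²) − m²
- SE = √[(v + 361)/23]
- power ≈ Φ[(m − 28)/SE − 1.96]

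| Lost (k) | Mean | SD | (m − 28)/SE | Power |
|---|---|---|---|---|
| 0 | 60.0 | 32.0 | 4.12 | 98.5% |
| 3 (13%) | 52.2 | 36.0 | 2.85 | 81% |
| 5 (22%) | 47.0 | 37.6 | 2.16 | 58% |

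So the loss of about one conduit in eight would usually still leave a significant flow advantage.

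**3. If lost conduits are dropped.** Provided that loss is unrelated to the flow the conduit would have had, the expected mean stays at 60. With 20 vs 23 readings, SE = √(1024/20 + 361/23) = √66.9 = 8.18, and 32/8.18 = 3.91. Power is Φ(3.91 − 1.96), about 97%. The harm leaves almost no trace in the flow result.

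**4. Dependence on the planning values.** The Review of Literature also gives 68 (46) vs 53 (32) mL/min. With those values and no losses, SE = √[(2116 + 1024)/23] = 11.7, 15/11.7 = 1.28, and power is about 25%. Step 2 therefore illustrates what the plan's own sample-size assumption implies. It is not a forecast.

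**5. What 23 per arm can say about harms.** With zero events, the one-sided 95% upper bound is 1 − 0.05^(1/n): 12.2% for n = 23, 10.1% for the 28-patient series and 0.85% for the 350-patient series. The last two belong to a different technique. The upper limit of the two-sided 95% interval for 0 of 23 is 1 − 0.025^(1/23) = 14.8%.

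**The case against.** **Flow already measures the motivating problem.** The protocol ties spasm and injury to poor flow, and flow is the basis of the sample size. The hypothesis asks for better flow as well as less time, so speed alone would not satisfy it, and injury severe enough to cut flow would count against the technique. This stands. A reader might infer that a faster but more injurious technique would necessarily be declared better, or that the trial gives no information on the problem it addresses. The documents support neither. What remains is the three gaps listed above.

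**Harms may be recorded on the proforma.** Its fields are not shown, and part of the document was not available for review. It therefore cannot be said that injury will never be counted. What can be said is that the text names no harm as an outcome and plans no comparison of one. Nor does the generic chi-square rule prove that an outcome is missing, since it may serve baseline items.

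**The trial is too small to compare harms.** This largely stands. A reader might take the 40% as a baseline rate and conclude that an injury comparison would be informative with 23 per arm. But the 40% combines damage with poor flow, and the documents give no rate for injury alone. The result also turns on assumed comparators. By exact enumeration (uncorrected chi-square / Fisher), power is 69% / 57% for 40% vs 10%, but only 32% / 22% for 40% vs 20%, and 19% / 10% for an excess harm of 5% vs 15%. That argues for descriptive reporting, but it is no reason to leave harms out.

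**The aim is deliberately narrow.** It is, and the plan already lists small sample size and skill dependence as limitations. But the harms are the protocol's own, and recording them costs little.

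**Conclusion.** The concern holds in a limited form. The text names three harvest harms, makes none of them an outcome and plans no comparison by arm. Because flow captures injury only partly, carbodissection could, not would, be reported as better despite more harm.

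The 81% power with 3 of 23 conduits lost rests on the planning means and SDs, losses in the carbodissection arm only, zero-flow scoring and a normal approximation. Dropping lost conduits would hide the loss more completely.

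The planned flow and time analyses are not invalidated. What would lack support is any general conclusion that the technique is better or as safe: even with no events in 23 patients, a true rate of up to about 12% could not be excluded.

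**What to change.** Add the following to the Objectives and the proforma, recorded identically in both arms:

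- **At harvest:** LIMA injury under a written definition (for example visible dissection, haematoma or a repair), LIMA not used as the graft, conversion from the allocated technique, and thoracic wall damage.
- **From routine inpatient notes to discharge:** sternal wound infection and re-exploration for bleeding.

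Report each by randomised arm as counts and percentages with exact 95% confidence intervals. Keep this descriptive, with no claim of equal safety.

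State in advance how an injured or discarded conduit with no reading enters the flow analysis. One option is to keep it in its randomised arm with flow set to zero, with a sensitivity analysis that excludes it.

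State the limit of the evidence: 0 of 23 excludes only rates above about 12% (one-sided 95%), or 14.8% as the upper limit of the two-sided 95% interval.

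**Cost.** A few fields taken from the operation note and inpatient record, one more table and a more cautious conclusion. No extra patients, visits, procedures or staff are needed. Two weaknesses remain and must be reported: injury would be assessed unblinded, and infections after discharge would be missed. If the proforma already holds these fields, only the definitions, the missing-reading rule and the reporting plan need adding.
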